4.3 Appropriateness of Measures

Multiple study sites are required to ensure efficient recruitment of subjects. Medical centers with well-established concussion research programs and referral populations have been selected to ensure subjects have access to appropriately trained and qualified healthcare providers.

The study is randomized to avoid the bias of subject selection for factors known and unknown between the treatment groups.

Randomization will be stratified by site and baseline symptom severity score on the PCSS (threshold $<$ or ≥ 30).

All assessments proposed in this study are considered by ANSwers Neuroscience Pty Ltd and the Investigators to be appropriate and necessary to compare graded exercise to passive stretching in post-mTBI recovery.

The PCSS is a well validated 21-item self-report measure that records symptom severity using a 7-point Likert scale of severity. This widely used symptom checklist ranks concussion symptoms by their severity and persistence.

Assessments used in this study to assess autonomic function include the BCBT, which measures the exacerbation of post-concussive symptoms during 15 minutes of step-wise escalation of cardio-vascular function and the cold pressor test (known as the “ice bucket test”), which has been shown to be diagnostic of mTBI. The BCBT has been validated against the BCTT, which has been shown to be diagnostic of mTBI, and to be predictive of PPCS.

The safety assessments used in this study such as adverse events (AEs) identified during graded exercise or passive stretching during the 20 minutes of daily therapy from Day 1 through Day 56, remote monitoring of vital signs including beat to beat blood pressure (BP), and daily self-reporting of symptoms on the PCSS are considered appropriate for monitoring subject health and well-being in this type of study.

In collaboration with a private diagnostic laboratory (Monogram Biosciences, a Division of Labcorp) who have validated a set of biomarkers reflective of the severity of mTBI assay structural proteins [t-tau, NF-L, GFAP and UCH-L1] and inflammatory cytokines [IL-6, IL-10 and TNF α]) will be analyzed. Blood and saliva samples will be collected at the time of enrollment and at the end of the study.

In addition, a set of single nucleotide polymorphisms (SNP) and micro ribonucleic acids (RNA) that have been implicated in contributing to the biologic vulnerability to PPCS will be analyzed. Deoxyribonucleic acid (DNA) and RNA will be isolated for bio-banking and subsequent analysis. Sample collection will be either blood collection or buccal swab and collection of saliva.

New tests, ClearHeart© and ClearNeck© will be validated as part of the study objectives by comparing against the equivalent validated methods, Ice Bucket Testing and neurological examination respectively, which will be also be performed as part of the study.

5 STUDY ENROLMENT AND WITHDRAWAL

5.1 Inclusion Criteria

To be eligible for study entry subjects must satisfy all of the following criteria:

1. Male or female subjects aged ≥ 14 to ≤ 45 , able and willing to provide informed consent (≥ 18 years), or informed consent is obtained by the parent or legal guardian for minor subjects, with the minor providing age appropriate assent, according to local law and regulations;

2. Subject is fluent in English, able to understand and agree to comply with protocol requirements, and complete all assessments;
3. Subject has a history of recent concussion as diagnosed by a health care professional within 3 to 14 days of enrolment;

Note: Concussion is defined as a head injury/blow to the head resulting in any of the following 3 signs and/or new symptoms: (1) amnesia for less than 24 hours; (2) Loss of consciousness for less than 30 minutes; (3) Glasgow Coma Scale score ≥ 13 ; (4) Dazed and Confused/bell rung; with at least 1 new symptom or augmentation of a previous symptom on the PCSS as compared with baseline at the time of enrolment, including: headaches, dizziness, fatigue, irritability, insomnia, difficulty concentrating, and/or memory difficulties; (5) The composite symptom score on the PCSS must be at least 3 points higher post-concussion than pre-concussion.

4. Subject has daily access to the internet.

5.2 Exclusion Criteria

Subjects will be excluded from the study if one or more of the following criteria are applicable:

1. History of prior head injury as defined by:
 - An injury/blow to the head within 12 months prior to screening with any associated residual symptoms;
 - An injury/blow to the head within 3 months prior to screening diagnosed as a concussion;
 - An injury/blow to the head within 3 months prior to screening with any of the following symptoms: amnesia, loss of consciousness, dazed and confused/bell rung;
2. Evidence of blood or micro-hemorrhages on prior or current computed tomography scan or magnetic resonance imaging scan if obtained;
3. Diagnosis of a neurological condition including the following: stroke, multiple sclerosis, epilepsy, brain tumor/cancer, encephalitis, dementia, movement disorder, or spontaneous nystagmus;
4. Psychiatric history with any of the following:
 - History of psychiatric hospitalization, history of legal trouble for violence;
 - Requires psychotropic medication other than (1) stable dose of a selective serotonin reuptake inhibitors (SSRI) medication, or (2) stable dose of a tricyclic antidepressants (TCA) medication;
 - Prior diagnosis of psychotic disorder, bipolar disorder, eating disorder, substance abuse disorder;

5. Current use of a beta blocker;
6. History of drug or alcohol dependency or abuse within a year before Screening, by self-report;
7. Two or more of the following cardiovascular risk factors:
 - Prior diagnosis of, or currently taking medication for cardiovascular, metabolic or pulmonary conditions;
 - Family history of myocardial infarction, coronary revascularization or sudden death before 55 years;
 - Diagnosis of hypertension;
 - Diagnosis of hyperlipidemia;
 - Subjects with peripheral circulatory disorders;
8. Subjects who are unable or unwilling to exercise for health or personal reasons;
9. Subjects who have musculoskeletal injuries which could make exercise difficult or painful.

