2.4 Known and Potential Risks

Potential risks exist to the following groups of patients:

- Subjects with musculoskeletal or cardiac or pulmonary conditions that preclude participation in exercise;
- Subjects using anti-hypertensive medications;
- Subjects with peripheral circulatory disorders due to conditions such as, but not limited to, Raynaud's syndrome, scleroderma, or diabetes. These subjects may experience hand discomfort when exposed to the ClearHeart© cooling;
- Subjects with lymphedema in the left arm, as they may experience arm discomfort when using the ClearHeart© device.

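### Two groups that Section 2.4 warns may have discomfort from ClearHeart are not clearly excluded, yet Section 4.1 requires ClearHeart before randomization and no waiver is given (minor)

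*Protocol*

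**What the plan says.** Section 2.4 of the protocol lists four groups at potential risk. Two are tied to ClearHeart. The first is "Subjects with peripheral circulatory disorders due to conditions such as, but not limited to" Raynaud's syndrome, scleroderma or diabetes, with the comment "These subjects may experience hand discomfort when exposed to the ClearHeart© cooling". The second is "Subjects with lymphedema in the left arm, as they may experience arm discomfort when using the ClearHeart© device".

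In Section 5.2, and likewise in the synopsis, exclusion 7 applies to a person with "Two or more of the following cardiovascular risk factors". The fifth and last factor on that list is "Subjects with peripheral circulatory disorders". Lymphedema appears in no inclusion or exclusion criterion.

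Section 4.1 allows randomization only after all baseline physiologic tests are done on Day 0, and it names the ice bucket test, ClearHeart and the bicycle test. Section 6.3.2 repeats the rule, and Table 4 puts both cold tests before randomization for odd and even subject numbers alike. Section 7.5.1 cools the left hand for 120 seconds in each cold test. Table 5 schedules both tests again at Day 56.

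**The concern.** The protocol identifies two groups for whom one of its own tests may be uncomfortable, then requires that test of everyone who is to be randomized. The eligibility rule that comes closest is a count of cardiovascular risk factors. A two-factor threshold suits a general cardiac screen. It does not suit a local reaction to cold that a single condition can bring about.

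What is at stake is tolerability and clear instructions to sites. A site that meets such a subject finds no named exclusion to apply, and no permission to leave out the cooling and still randomize.

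**Working it through.** No figure in the plan is in question, so the check sets the sections side by side.

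**Step 1: each risk group in Section 2.4 against Section 5.2**

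| Group in 2.4 | Matching exclusion | Coverage |
|---|---|---|
| "Subjects with musculoskeletal or cardiac or pulmonary conditions that preclude participation in exercise" | 8 ("Subjects who are unable or unwilling to exercise for health or personal reasons") and 9 ("Subjects who have musculoskeletal injuries which could make exercise difficult or painful") | Stand-alone |
| Users of anti-hypertensive drugs | 5 (beta blockers only); hypertension is one factor in 7 | Partial |
| Peripheral circulatory disorders | One factor in 7 | Partial: 1 of 5 factors, 2 needed |
| Left-arm lymphedema | None | 0 of 9 criteria |

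**Step 2: the exclusion 7 count for typical cases** (threshold 2)

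- Peripheral circulatory disorder as the only factor, such as primary Raynaud's: count 1, and 1 < 2, so not excluded on a plain reading. A site might also count the disorder as a cardiovascular condition under the first factor, which would give 1 + 1 = 2. That depends on interpretation, hence not clearly excluded.
- Diabetes with a peripheral circulatory disorder: metabolic condition (1) + circulatory disorder (1) = 2, so already excluded.
- Left-arm lymphedema alone: count 0, and no other criterion applies.

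**Step 3: the exposure**

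- Each visit has 2 cold tests of 120 seconds, one of them ClearHeart. Over Day 0 and Day 56 a completer has 2 × 2 = 4 coolings, of which 2 are ClearHeart (2 × 120 = 240 seconds).
- The cooled hand is the left, because the monitor sits on the right arm and finger. This is the side named in the lymphedema warning, and no alternative arm is offered.

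**Step 4: is there a way out of the test?**

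- Section 7.5.1 has no waiver and no stopping rule.
- Elsewhere the protocol does make such provisions: Section 7.5.2 gives termination rules for the bicycle test, and Section 7.2 offers a buccal swab and saliva to needle-phobic subjects.

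The gap is therefore the subject whose sole exclusion 7 factor is a peripheral circulatory disorder, and the subject with left-arm lymphedema.

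**The case against.** The strongest reply is that disclosing a risk does not commit the sponsor to exclude those who carry it. That stands. A reader might infer that Section 5.2 breaks a promise made in Section 2.4, but no such promise is made. The anti-hypertensive group is also only partly covered, so the clean match for the exercise group is not a general pattern.

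Three other stronger readings are tempting, and the protocol does not support them:

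- *Every subject with a circulatory disorder slips through.* The diabetic case in Step 2 shows otherwise.
- *The subjects face injury.* Section 2.4 speaks only of discomfort, and the exposure is two minutes.
- *The protocol flags the ice bucket as well.* It names ClearHeart alone. Extending the warning to ice water on the same hand is a reasonable inference, but only an inference.

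General safeguards also count. Inclusion 2 in the synopsis requires the ability to complete all assessments, so someone who cannot bear the cooling fails it. Consent covers risks (Section 12.4), subjects may withdraw at any time (5.3.1), and trained staff monitor risk (2.6). The Investigator's Brochure is not shown and may hold device precautions. The comparison with the bicycle test is imperfect too, since several of its termination rules are end points of an escalating test.

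These arguments limit the weight of the point but do not remove it. A person who will find the cooling uncomfortable may still be able to complete it, and so passes inclusion 2. None of the safeguards names either condition, and none lets a subject omit the cooling and still be randomized.

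**Conclusion.** The point holds as a minor mismatch between the risk statement and the eligibility and testing rules. A subject with a peripheral circulatory disorder as the only exclusion 7 factor, or with left-arm lymphedema, is not clearly excluded and cannot be randomized under Section 4.1 without the cooling that Section 2.4 warns about.

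Its size cannot be put in numbers of subjects, because the protocol gives no prevalence for either condition. There is no effect on the symptom-based primary endpoint or the sample size. The conclusion rests on a plain reading of exclusion 7, in which a circulatory disorder counts once, and on the protocol alone; a precaution in the Investigator's Brochure could narrow the gap.

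**What to change.** Either of two wording changes would do.

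1. **Exclude.** In Section 5.2 and the synopsis, take peripheral circulatory disorders out of the two-of-five count and make them and left-arm lymphedema stand-alone exclusions. Cost: a few subjects not enrolled, and a slightly narrower population than the broad one Section 2.5 aims for.
2. **Waive.** In Section 7.5.1 and Table 5, let these subjects skip ClearHeart, and say in Sections 4.1 and 6.3.2 and in Table 4 that they may still be randomized. Cost: a few pairs lost to the Bland-Altman comparison of ClearHeart with the ice bucket, and a few ClearHeart values lost to the cold pressor summaries in Section 9.6.2.

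The sponsor may choose to waive the ice bucket as well. That costs more: those subjects' ice bucket data are also lost to the composite physiologic metric (Table 1), to the blood pressure balance check in Section 9.6, and to the vital signs that Section 7.1.4 collects around the cooling.

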5.3 Withdrawal and Replacement of Subjects

5.3.1 Reasons for Withdrawal of Subjects

Subjects will be informed that they have the right to withdraw from the study at any time for any reason, without prejudice to their medical care. The investigator also has the right to withdraw subjects from the study for any of the following reasons:

- Subject non-adherence to therapeutic intervention or protocol requirements. Please refer to Section 6.5 for lifestyle and dietary study restrictions. Subjects must also be able to upload data via the ClearPlay© mobile application daily. Failure to do so for 3 consecutive days will trigger a call from the site. Subjects who do not upload data for 5 consecutive days are to be contacted by the site again. Subjects who do not upload for 7 consecutive days are to be withdrawn from the study for poor compliance;
- Subjects from either group who exercise at a rate that exceeds that which is prescribed, as identified by either self-report (the Godin Leisure Time Exercise questionnaire) or by autonomic monitoring (using ClearPlay©) will be withdrawn from the study and coded as “lost to follow up”.
- Subject unwillingness to continue in the study;
- Any other reason based upon the medical judgment of the investigator.

The reason for study withdrawal is to be documented in the subject’s source documents and electronic case report form (eCRF).

At the time of discontinuation from the study, subjects are to have all the assessments planned for the follow-up visits performed after the last study drug dose, if feasible.

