5.3.2 Handling of Withdrawals or Early Termination of Subjects

Withdrawals or early termination: If a subject is withdrawn from the study for any reason, whether related to the study drug or not, or if a subject voluntarily withdraws, such subject will be considered an early termination subject. The investigator will make every effort to ensure that early-termination subjects complete an Early Termination visit.

Lost to follow-up: Reasonable efforts will be made to contact subjects who are lost to follow-up. These efforts must be documented in the subject's file.

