9.6 Efficacy Analysis

The full presentation of the analysis of efficacy data will be presented in the SAP.

For all subjects, daily reported PCSS scores collected from ClearPlay© mobile application will be utilized to determine the resolution of symptoms. The resolution of symptoms is defined as a symptom-severity score of less than each subject's pre-injury PCSS score for 3 consecutive days. To assess differences in the probability of symptom resolution between graded exercise and passive stretching during the 8 weeks of therapy, both unadjusted and adjusted logistic regression models will be used. The primary outcome of the study will be to confirm or refute the superiority of sub-threshold aerobic exercise versus passive stretching to result in resolution of symptoms following mTBI. Confounders for the adjusted models will include age, gender, anxiety at baseline, history of migraine, cardiovascular fitness, the presence or absence of neurologic findings, and site of enrollment.

The survival probability will be compared using Kaplan-Meier (log rank test) analyses between the 2 treatment arms. Cox proportional hazards regression models will be used to evaluate the differences in time to symptom resolution. Adjusted treatment effects will be estimated in Cox proportional hazards regression models, controlling for the variables listed above. To identify that our randomization strategy was effective, analysis of variance will be used to assess for group-wise differences in age, days since injury to initial visit, initial PCSS score, resting HR, and Δ HR during the BCBT and resting BP and Δ BP during the ice bucket test on Day 1. Non-parametric tests of medians will be used to compare the non-normally distributed variable duration of clinical recovery. Chi-squared tests will be used to assess group-wise differences in gender, history of concussions, and incidence of PPCS.

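### Section 5.3.1 removes over-exercising subjects from the study and codes them lost to follow-up, which conflicts with 5.3.2 and stops the daily PCSS behind the primary outcome

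*Protocol*

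**What the plan says.** Section 5.3.1 lists reasons for which the investigator may withdraw subjects. One bullet is worded as mandatory and covers "Subjects from either group who exercise at a rate that exceeds that which is prescribed". Detection rests on either of two sources, the weekly Godin entries or ClearPlay monitoring. The stated consequence is that such a subject "will be withdrawn from the study and coded as" lost to follow-up. The same section then requires the reason for withdrawal to be documented in the source and the eCRF.

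Section 5.3.2 sets up two classes. For withdrawal from the study, whatever the reason, the rule is that "such subject will be considered an early termination subject", and the investigator is to try to obtain an Early Termination visit. The other class is dealt with by contact attempts: "Reasonable efforts will be made to contact subjects who are lost to follow-up".

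Section 9.6 states that daily PCSS scores from the app "will be utilized to determine the resolution of symptoms", defined as three consecutive days below the pre-injury score. For the probability of resolution over the 8 weeks, "both unadjusted and adjusted logistic regression models will be used"; time to resolution is compared by log-rank test and Cox regression. Section 9.8 uses a withdrawn subject's data up to withdrawal, with no imputation unless otherwise stated. Table 5 marks the PCSS at baseline and over Day 1 to Day 55, but not at the Follow-Up/ET visit.

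**The concern.** There are two problems.

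The first is classification. The same subject is lost to follow-up under 5.3.1 and early termination under 5.3.2. Someone identified from their own Godin entries or app monitoring is in contact with the study, and the reason for removal is known. The disposition summary in 9.4 would show a removal required by the protocol as loss of contact, and sites could class identical cases differently.

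The second is loss of the outcome. The subject leaves the study, not only the intervention, so PCSS entry stops. The trigger is behaviour after randomisation in an open-label trial. It plausibly tracks symptoms, and the prescribed activity differs by arm (Table 2). If removal is related to outcome and unequal between arms, the primary comparison is biased. The direction cannot be stated: over-exercisers may be fast recoverers, or slow ones, since Section 2.3 links intensive exercise too early to delayed recovery.

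**Working it through.** **Can other data replace the lost scores?** The Follow-Up/ET column of Table 5 has no PCSS, and one visit cannot show three consecutive days. The paragraph of 9.8 that keeps subjects in all analyses concerns withdrawal from the intervention; this rule withdraws them from the study. Subjects who met the three-day definition before removal keep their event, so only those still unresolved are affected.

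**The plan's own figure.** Section 9.1 gives 80% versus 93%, 90% power and α = 0.05. Two-sided, with mean proportion 0.865:

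- n = [1.96·√(2·0.865·0.135) + 1.2816·√(0.80·0.20 + 0.93·0.07)]² / 0.13² = 143.1 per arm.
- Continuity correction: (143.1/4)·[1 + √(1 + 4/(143.1·0.13))]² = 158.1 per arm, or 316 in total when rounded to 158 (318 when rounded up). The stated 316 reproduces.
- Attrition: 316 × 1.15 = 363.4, the stated 363.
- Planned margin: (200 − 158)/200 = 21% per arm.

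The larger sample covers a loss of numbers. It does not correct bias.

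**False positives with no true effect.** Assumptions: exponential time to resolution in whole days, 80% resolved by day 56 in both arms, 200 per arm, |z| > 1.96, 6,000 simulated trials per scenario (standard error near 5%: √(0.05·0.95/6000) = 0.28 points). Outcome-related withdrawal means the stated share of would-be resolvers is censored 1–7 days before resolution. Random withdrawal means the stated share of all subjects is removed at a uniform time over days 1–56, counting only before their own resolution. Shares are stretching/exercise, in percent.

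| Shares, all outcome-related | Log-rank rejection (favours exercise / stretching) |
|---|---|
| 0/0 | 5.1% (2.5/2.5) |
| 10/10 | 5.2% (2.6/2.6) |
| 3/1 | 5.3% (3.5/1.8) |
| 5/2 | 5.8% (4.3/1.5) |
| 2/5 | 6.0% (1.2/4.7) |
| 5/0 | 7.3% (6.5/0.8) |
| 10/5 | 7.4% (6.4/0.9) |
| 10/0 | 13.3% (13.0/0.3) |
| 15/5 | 13.4% (13.2/0.2) |
| 5/15 | 13.2% (0.2/13.0) |
| 0/10 | 13.6% (0.2/13.4) |

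At a 10-point gap with half the withdrawals outcome-related the rate is 7.0–7.9%; with a quarter, 5.4–5.7%. Random timing gives 4.8–5.3%. Repeat runs of the model gave 6.4% at 5/2, 7.0% at 10/5 and 13.7% at 15/5.

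**Unadjusted logistic comparison** (score test, i.e. pooled two-proportion z). The result depends on how withdrawn subjects are scored:

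- Left out: 4.4–7.7% in the scenarios above. If withdrawals come instead from slow or non-resolvers, the result depends on how that is modelled: one run gave 5.0–8.6% (log-rank 4.8–7.8%); another gave 11–12% at 10-point gaps (log-rank 8–9%) but 5–6% at 3/1 and 5/2.
- Counted as unresolved: 5.2–9.1% at small gaps (3/1, 5/2, 2/5); at 10-point gaps 10.2–11.6% (random), 23.9–25.4% (half outcome-related) and 42.4–47.4% (all outcome-related).

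A closed-form check on that last scoring: if shares w_s and w_e are all removed before resolution and would have resolved with probability r, the false difference is (w_s − w_e)·r. At 15/5 this is 0.10·0.80 = 8 points to 0.10·1.00 = 10 points, with a 43–59% chance of a significant result. The simulated random-timing figure is lower because many subjects resolve before their withdrawal time.

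**Power at 80% versus 93%** (4,000 trials per scenario). Log-rank: 99.6% without withdrawals, 95.0% at worst (5/15, all outcome-related). Logistic: 97.5% without withdrawals; 93.2–99.0% with withdrawn subjects left out; counted as unresolved, 94.8% (random) to 77.2% (all outcome-related) at 2/5, and 81.1% to 11.7% at 5/15.

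**The case against.** - **The labels may not exclude each other, and the reason is recorded anyway.** One label could govern the visit and the other the code. But 5.3.2 handles lost to follow-up as a separate class by contact attempts, and a duty to record the true reason sits badly beside a code that misstates it.
- **Withdrawal may be discretionary.** The lead-in to 5.3.1 gives the investigator a right, not a duty. That does not cancel the mandatory wording of the bullet; it adds another ambiguity to resolve.
- **Unequal triggering is inferred.** This stands in part. Section 6.7 sets the same limit on outside exercise in both arms, and Table 2 gives no rates. Only the in-session prescription differs, so a gap between arms is plausible but undocumented.
- **The log-rank test is robust.** This largely stands. If fast recoverers are flagged anywhere from 7 days before to 7 days after resolution, the rate is 4.2–6.5% even at 10-point gaps, because those already resolved keep their event.
- **The largest figures need a scoring rule the protocol does not state.** This stands. Counting withdrawn subjects as unresolved is not specified, 9.8 says no imputation unless otherwise stated, and scoring belongs to the analysis plan. Those figures show sensitivity, not an expected error.
- **If few subjects are affected, so is the result.** Also correct: few and nearly balanced means 5.3–6.0% for the log-rank test.
- **Retained scores will reflect off-protocol exercise.** True, and it is the price of keeping randomised subjects in the comparison.

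**Conclusion.** The concern holds. Whatever the frequency of over-exercise, the code is wrong for reachable subjects and conflicts with 5.3.2, and the rule as written ends collection of the only data that establish resolution. This should be fixed.

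The likely bias is a separate and weaker statement. The protocol gives no withdrawal rate, imbalance or direction. Under the assumed scenarios with withdrawals shortly before resolution or at random times, the log-rank test stays close to nominal for balanced, random or small-gap withdrawals. It reaches 7.3–7.4% at a 5-point gap with all withdrawals outcome-related. About 13% requires a 10-point gap (16 of the 0.80 × 200 = 160 would-be resolvers in an arm), every one removed in the week before resolution. The logistic comparison is more exposed if withdrawn subjects count as unresolved. Confidence is high on the contradiction and the data loss; material bias is possible, not shown.

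**What to change.** - In 5.3.1, separate leaving the study from any decision about the intervention. The protocol already does this elsewhere: 6.1 keeps subjects who have ceased the intervention in the study to Day 56, and 6.5.1 records prohibited medication as a deviation.
- Record excess exercise as a protocol deviation with its true reason. Keep lost to follow-up for subjects who cannot be contacted.
- Continue daily app PCSS through Day 55 for consenting subjects, and keep the Day 56 visit for the other scheduled measures.
- Include these subjects in the primary analysis in their randomised arm, with censoring at the deviation as a sensitivity analysis.
- Reconcile 5.3.1, 5.3.2, 9.3.3 (which analyses by actual therapy received) and 9.8.

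Whether therapy continues, and what exercise limit applies, remains for the sponsor and investigator.

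The cost is protocol wording, one eCRF reason code, and continued app entry and site review for the subjects concerned, who already have the device. The amendment needs sponsor and ethics committee approval (10.3). Some contamination stays in the main estimate; the sensitivity analysis would help show how far the result depends on it.
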